## 12.4 Safety

Safety data will be summarized by dose group and based on their initial dose level or treatment group (i.e., if a dose reduction occurs, they will be considered in their initial group). Descriptive statistics will be provided for actual values and change from baseline values for vital signs, weight, blood parameters, ECG (QT).

AE assessment and treatment area evaluation including, but not limited to evaluation of edema, bruising, dysphasia, dysphonia, erythema, dyspigmentation, induration, numbness, pain, paresthesia, and pruritus.

The incidence and severity of AEs reported during the study and their relationship to study drug will be tabulated. AEs will be coded using MedDRA™ and will be presented by body system. AEs will be graded according to the Common Terminology Criteria for Adverse Events (CTCAE) v 5.0 (Table 5).

The World Health Organization Drug Dictionary (WHODD) will be used to classify prior and concomitant medications by therapeutic class and preferred term. Prior and concomitant medication usage will be summarized by the number and percentage of subjects receiving each medication within each therapeutic class by dose cohort.

## **13.0 DATA COLLECTION, STUDY MONITORING, AND DATA DISCLOSURE**

### **13.1 Data Collection and Reporting**

An eCRF will be completed for each subject who receives at least one dose of study drug. All entries on the eCRF must be supported by original source documentation (e.g., laboratory reports, medical records) maintained at the investigational site.

The Investigator will make all safety assessments (AEs and vital signs) on an ongoing basis. The Investigator is required to review all entries on the eCRF and sign at appropriate time intervals.

### **13.2 Study Monitoring**

All aspects of the study will be monitored carefully by the Sponsor's designees with respect to current Good Clinical Practice (GCP) and Standard Operating Procedures (SOP) for compliance with applicable government regulations. It is the responsibility of the Investigator to provide all study records, including eCRFs, source documents, etc., for review and source document verification by the clinical monitor.

All eCRFs will be 100% source verified against corresponding source documentation (e.g., office and clinical laboratory records) for each subject. Clinical monitors will evaluate periodically the progress of the study, including the verification of appropriate consent form procedures, review of drug accountability and preparation procedures, adherence to dosing procedures, and the verification of the accuracy and completeness of eCRFs. Clinical monitors will also ensure that all protocol requirements, applicable FDA regulations, other requirements, and Investigator's obligations are being fulfilled.

### **13.3 Audit and Inspection**

The sponsor or representative may conduct audits at the trial site(s). Audits will include, but are not limited to protocol compliance, drug supply, presence of required documents, the informed consent process, and comparison of eCRFs with source documents. The investigator agrees to participate with audits conducted at a reasonable time in a reasonable manner.

Regulatory authorities worldwide may inspect the trial site during or after the trial. The investigator should contact the sponsor immediately if this occurs and must fully cooperate with the inspections conducted at a reasonable time in a reasonable manner.

### **13.4 Deviation from Clinical Trial Protocol**

Deviations from the protocol are to be avoided. If a deviation occurs, the Investigator must promptly report the deviation to the study monitor.

The Investigator (or designee) will record any failure to follow the protocol because of any other medical unavoidable reason to avoid the subject's urgent risk, and record a document as soon as

possible stating this and the reason. It must be submitted to the sponsor and the director of the study site.

### **13.5    Retention of Records**

The Investigator must retain all study records required by Raziel and by the applicable regulations in a secure and safe facility. The Investigator must notify Raziel of any change in the location, disposition or custody of the study files. The Investigator/institution must take measures to prevent accidental or premature destruction of essential documents, that is, documents that permit evaluation of the conduct of a study and the quality of the data produced, including paper copies of study records (e.g., subject charts) as well as any original source documents that are electronic as required by applicable regulatory requirements.

All study records must be retained until whichever is the later day in the following: (1) At least the date of approval for the drug or (2) the date when 3 years have passed since the discontinuation or completion of the study. No records relating to this study should be disposed of without the written approval of Raziel. It is the responsibility of Raziel to inform the Investigator/institution as to when these documents no longer need to be retained.

### **13.6    Data Disclosure and Subject Confidentiality**

Subject medical information and video recordings obtained as a result of this study is considered confidential and used only for study evaluation purposes. Disclosure to third parties other than those noted below is prohibited. All reports and communications relating to subjects in this study will identify each subject only by number. Medical information resulting from a subject's participation in this study may be given to the subject's personal physician or to the appropriate medical personnel responsible for the subject's welfare. Data generated as a result of this study are to be available for inspection on request by FDA or other government regulatory agency auditors, the Sponsor clinical monitor (or designee), and the IRB/EC.

All laboratory specimens, evaluation forms, reports, and other records that leave the site will be identified by a coded number to maintain subject confidentiality. All records will be kept in a locked and secured area. All computer entry and networking programs will be identifiable only by coded numbers. Clinical information will not be released without written permission from the subject, except as necessary for monitoring by the IRB, the FDA, or the study Sponsor.

Any information, inventions, or discoveries (whether patentable or not), innovations, suggestions, ideas, and reports, made or developed by the Investigator(s) as a result of conducting this study shall be promptly disclosed to the Sponsor and shall be the sole property of the Sponsor. The Investigator agrees, upon the Sponsor's request and at the Sponsor's expense, to execute such documents and to take such other actions, as the Sponsor deems necessary or appropriate, to obtain patents in the Sponsor's name covering any of the foregoing.

The results of this study will be published under the direction of the Sponsor. Results will not be published without prior review and approval by the Sponsor and Study Investigator.

## **14.0 PROTECTION OF HUMAN SUBJECTS**

### **14.1 Basic Principles**

The study will be conducted in accordance with the relevant regulatory requirements, this protocol, and ethical principles that are consisted with the GCP guideline developed by the International Conference on Harmonization of Technical Requirements for Registration of Pharmaceuticals for Human Use (ICH). This clinical trial will also be conducted in compliance with Declaration of Helsinki, protocol, Standard specified in the relevant local regulations. Prior to initiation of the study, the investigator and the sponsor should obtain approval from the IRB/IEC on this protocol and any further amendments, and the subject information and informed consent form.

Any suspected serious breaches must be immediately reported to the sponsor. A serious breach is a breach of the conditions and principles of GCP in connection with the study or the protocol, which is likely to affect, to a significant degree, the safety of the subjects or the scientific value of the study.

Personnel involved in the study will be qualified by education, training, and experience to perform their respective tasks.

### **14.2 Institutional Review Board/Ethics Committee**

The Investigator or designee agrees to provide the IRB/EC with all appropriate material, including a copy of the ICF. The study will not be initiated until the Investigator obtains written approval of the research plan and the ICF from the appropriate IRB/EC and copies of these documents are received by the Sponsor. Appropriate reports on the progress of this study will be made by the Investigator to the IRB/EC and Sponsor in accordance with applicable government regulations and in agreement with the policies established by the Sponsor. The Sponsor ensures that the IRB/EC complies with the requirements set forth in 21 CFR Part 56 (Code of Federal Regulations).

### **14.3 Informed Consent**

The investigator is responsible for:

- Explain the subject of the study, the risks and benefits expected from participating in the study, and that the participation is voluntary so that the subject can understand.
- Obtain informed consent to participate in the trial from the subject by signing or signing the consent form and entering the date before starting the study procedure and study drugs.

- Properly answer questions from subjects at any time during the trial and if new information that can affect the subject's intention to continue the trial is obtained while the subject is participating in the trial, the information is promptly communicated to the subject.
- Give a copy of the written consent form to the study participants and keep one copy at the study site.

#### **14.4 Subject Health Injury and Insurance**

In general, if a subject is health-injured as a direct result of the investigational products, the sponsor or its contracted insurance company will pay for reasonable and necessary medical treatment for the health-injury. If laws or regulations of the locality in which the study is taking place require additional payment of expenses, the sponsor should comply with such laws or regulations. Where applicable, the sponsor will arrange for specific insurance coverage. If health damage occurred in subject participating the clinical trial due to the willful or gross negligence of investigator's site, indemnification will be discussed based on the contract with the site. The indemnification for the health damage and the payment to subjects will be described in the ICF.

#### **14.5 Completion of the Study**

If the clinical trial is completed at the study site, the investigator will notify the director of the study site that the trial has been completed and provide an approximate summary in writing. The director of the study site will promptly notify the IRB/EC and the Sponsor in writing about the completion.

## Appendix A: Schedule of Study Procedures

**Table 1: Schedule of Study Procedures**

[figure not shown]
Study Procedure	Screening Day	Baseline (Treatment)	Visit Schedule (Days 1 to 84)					Additional follow up of RZL-012 treated subjects (6 and 12 months after injection)	
			Day 1	Day 7	Day 28	Day 56	Day 84	6 months	12 months
Study Day a	Day (-28) through Day (-1)	Day a 0							
Signed informed consent	X								
Medical history	X								
Physical Exam b	X						X	X h	X h
Concomitant Medication	X	X	X	X	X	X	X		
Pregnancy β-hCG	X								
Pregnancy urine test (women) c		X							
Caliper measurement of submental fat	X				X	X	X		
Weight measurements	X	X				X	X		
Hematology and Chemistry d	X		X	X	X		X		
ECG	X			X			X		
Vital signs	X	Pre e X post e	X	X	X	X			
Injection of RZL-012		X							

Study Procedure	Screening Day	Baseline (Treatment)	Visit Schedule (Days 1 to 84)						Additional follow up of RZL-012 treated subjects (6 and 12 months after injection)	
			Day 1	Day 7	Day 28	Day 56	Day 84			
Study Day a	Day (-28) through Day (-1)	Day a 0								
Clinician Chin Assessment Tool (C- CAT)	X	X			X	X	X	X	X	X
Subject- Self-Chin Assessment Tool (S- CAT)	X	X			X	X	X	X	X	X
Physician Global Assessment Improvement Scale (GAIS) and physician global assessment	X				X	X	X			
Subject's Satisfaction questionnaire for SMF appearance	X g				X	X	X			
Subject's impact questionnaire	X				X	X	X			
Subject Global Assessment of Change and subject self assessment	X				X	X	X			

Study Procedure	Screening Day	Baseline (Treatment)	Visit Schedule (Days 1 to 84)						Additional follow up of RZL-012 treated subjects (6 and 12 months after injection)	
			Day 1	Day 7	Day 28	Day 56	Day 84	6 months	12 months	
Study Day a	Day (-28) through Day (-1)	Day a 0								
2D Standardized photography	X		X	X	X	X	X	X	X	
MRI	X f						X			
AEs		X	X	X	X	X	X	X	X	

- a. Study day is based on Day 0 defined as the day of RZL-012 injection.
- b. Including Fitzpatrick skin type, height, BMI
- c. A serum ( $\beta$ -hCG) pregnancy test will be administered to females of childbearing potential at screening and a urine pregnancy test will be administered at baseline prior to dosing
- d. In case of clinically significant values at any visit, an unscheduled visit will be added
- e. Pre/post – refers to before/after injection, respectively
- f. MRI (performed during screening period) will be conducted after subject qualifies on all screening criteria. Post-treatment period MRI will be completed 84 days ( $\pm$  14 days) after the subject's last treatment session.
- g. Subjects will be asked on their neck appearance satisfaction at screening visit
- h. Physical exam will be done only to the treated area

## Appendix B: Photographic Standards of the Face Area

## Appendix C: Clinician Chin Assessment Tool

RZL-SFSD-US-001\_C  
-CAT.pdf

## Appendix D: Subject Chin Assessment Tool

RZL-SFSD-US-001\_S  
-CAT.pdf

## 1. DEFINITIONS AND/OR ABBREVIATIONS

ADR	Adverse drug reaction
AE	Adverse event
BMI	Body Mass Index
C-CAT	Clinical Chin Assessment Tool
cGMP	Current Good Manufacturing Practices
CI	Confidence Interval
CRF	Case Report Form
ECG	Electrocardiograms
GAIS	Global Aesthetics Improvement Scale
ICF	Informed Consent Form
ICH-GCP	International Conference on Harmonization Good Clinical Practice
IRB	Institutional Review Board
ITT	Intent-to-Treat
MedDRA	Medical Dictionary for Regulatory Activities
MRI	Magnetic Resonance Imaging
NOAEL	No observed adverse effect level
PI	Principal Investigator
PP	Per-Protocol
QA	Quality Assurance
QOL	Quality of life
S-CAT	Subject Self-Chin Assessment Tool
SAE	Serious adverse event

SAP	Statistical Analysis Plan
SAS	Statistical Analysis Software
SMF	Submental fat
TEAE	Treatment emergent adverse event(s)
US/USA	United States/United States of America
WHO	World health organization

	DOCUMENT NUMBER: 140-BST-PLN-001	PAGE: 7 of 16
TITLE: Statistical Analysis Plan of Protocol Number RZL-012-SMF-P2bUS-001	EFFECTIVE DATE : 08/03/2022 REVISION NUMBER : 1.0	

## 2. PURPOSE

The purpose of this statistical analysis plan (SAP) is to describe in detail the statistical analyses to be conducted by Medistat Ltd on data generated from the clinical trial sponsored by Raziel Therapeutics Ltd. (clinical trial **RZL-012-SMF-P2bUS-001**).

This SAP aims to provide details on: sample size calculation, efficacy analyses and safety analyses.

## 3. SCOPE

This document applies to all members of the statistical & data management units in Medistat Ltd.

This document includes the main study trial analyses.

### Raziel Therapeutics's Responsibilities

To review and approve the SAP and related documents prior to database lock

MediStat Statistics in Medicine	DOCUMENT NUMBER: 140-BST-PLN-001	PAGE: 8 of 16
TITLE: Statistical Analysis Plan of Protocol Number RZL-012-SMF-P2bUS-001	EFFECTIVE DATE : 08/03/2022 REVISION NUMBER : 1.0	

## 5. PROCEDURE

- **Introduction**

This Statistical Analysis Plan (SAP) is based on **RZL-012-SMF-P2bUS-001** study protocol version 1.6, dated 08 March 2022

This Statistical Analysis Plan (SAP) contains details of the statistical analyses that will be performed, providing a more detailed description of the approach defined in the study protocol. Definitions of variables and populations used for the analyses are also included. The SAP will be finalized and signed prior to hard lock of the database.

General output specifications are provided; examples are given of calculations of derived variables.

- **Study Objectives and Endpoints**

### Primary Objective

To determine the efficacy of RZL-012 versus placebo on submental fat (SMF) reduction measured on Day 84 versus baseline using the Clinician Assessment Tool (C-CAT).

### Secondary Objectives

To determine the efficacy of RZL-012 versus placebo on SMF reduction measured on Day 84 versus baseline using both the Subject Self-Chin Assessment Tool (S-CAT) and the Clinician Assessment Tool (C-CAT);

To assess the reduction in SMF on Day 84 versus baseline using the caliper measured submental thickness and magnetic resonance imaging (MRI);

To assess the safety of RZL-012 in the treatment of SMF reduction.

### Primary Endpoint

Comparison of the proportion of subjects who have at least a 1-grade improvement in the C-CAT on Day 84 versus baseline between the RZL-012 high dose (270 mg/5.4 mL) group and the placebo group.

### Secondary Endpoints:

MediStat Statistics in Medicine	DOCUMENT NUMBER: 140-BST-PLN-001	PAGE: 9 of 16
TITLE: Statistical Analysis Plan of Protocol Number RZL-012-SMF-P2bUS-001	EFFECTIVE DATE : 08/03/2022 REVISION NUMBER : 1.0	

- Proportion of subjects who have at least a 1-grade improvement in both the C-CAT and S-CAT (Day 84 versus baseline) in the RZL-012 groups versus placebo group.
- Proportion of subjects who have at least a 2-grade improvement in both the C-CAT and S-CAT (Day 84 versus baseline) in the RZL-012 groups versus placebo group.
- Reduction in SMF volume by MRI (Day 84 versus screening) in the RZL-012 groups versus placebo group.
- Reduction in SMF thickness measured with caliper (Day 84 versus baseline) in the RZL-012 groups versus placebo group. Safety assessment of RZL-012 in the treatment of SMF reduction.
- safety of RZL-012 in the treatment of SMF reduction.

Exploratory endpoints:

- Physicians Global Assessment
- SMF improvement using the Global Aesthetic Improvement Scale (GAIS).
- Subject Global Self-Assessment
- SMF improvement using the Subject Global Assessment of Change Scale.
- SMF improvement using the subject's satisfaction questionnaires.
- SMF improvement using Subject's impact questionnaire.

- Study Design

This is a Phase 2b, double-blind, randomized, three-arm, placebo-controlled study that consists of a screening period, baseline period, and a randomized treatment period. Subjects receive a single treatment session that consists of multiple injections of RZL-012 or placebo into the submental area under the chin, after which they are monitored for safety and efficacy over 84 days.

Following the completion of Day 84 visit of the last subject, subjects from three (3) chosen clinical sites are followed up to a 1 year after injection to evaluate the long term safety and efficacy. The additional follow up visits are conducted at 6 and 12 months after injection.

Study participants are adult volunteers (135 subjects - 45 subjects per group) of 18 to 65 years of age who have consented to participate in this study. Each subject is randomized to either active treatment (high or low dose RZL-012) or placebo at a ratio of 1:1:1 per group and receives one of the following:

- low dose (concentration of injected solution 34 mg/mL RZL-012) of 5.1 mg/0.15 mL/injection point ( $32\pm4$  injection points) that results in an average total injected dose/volume of  $163.2\pm20.4$  mg/ $4.8\pm0.6$  mL RZL-012.

**TITLE:** Statistical Analysis Plan of Protocol Number **RZL-012-SMF-P2bUS-001**
**EFFECTIVE DATE :** 08/03/2022  
**REVISION NUMBER :** 1.0

- high dose (concentration of injected solution 50 mg/mL RZL-012) of 7.5 mg/0.15 mL/injection point (32±4 injection points) that results in an average total injected dose/volume of 240±30mg/4.8±0.6mL RZL-012.
- placebo of 0.15 mL/injection point (32±4 injection points) that results in an average total injected volume of 4.8±0.6mL.

- Schedule of Assessments

Study Procedure	Screening Day	Baseline (Treatment)	Visit Schedule (Days 1 to 84)					Additional follow up of RZL-012 treated subjects (6 and 12 months after injection)	
			Day 1	Day 7	Day 28	Day 56	Day 84		
Study Day a	Day (-28) through Day (-1)	Day a 0						6 months	12 months
Signed informed consent	X								
Medical history	X								
Physical Exam b	X						X	X h	X h
Concomitant Medication	X	X	X	X	X	X	X		
Pregnancy β-hCG	X								
Pregnancy urine test (women) c		X							
Caliper measurement of submental fat	X				X	X	X		
Weight measurements	X	X				X	X		
Hematology and Chemistry d	X		X	X	X		X		
ECG	X			X			X		
Vital signs	X	Pre e X post e	X	X	X	X			
Injection of RZL-012		X							
Clinician Chin Assessment Tool (C-CAT)	X	X			X	X	X	X	X

**TITLE: Statistical Analysis Plan of Protocol Number RZL-012-SMF-P2bUS-001**
**EFFECTIVE DATE : 08/03/2022  
REVISION NUMBER : 1.0**

Study Procedure	Screening Day	Baseline (Treatment)	Visit Schedule (Days 1 to 84)					Additional follow up of RZL-012 treated subjects (6 and 12 months after injection)	
			Day 1	Day 7	Day 28	Day 56	Day 84	6 months	12 months
Study Daya	Day (-28) through Day (-1)	Day a 0							
Subject- Self-Chin Assessment Tool (S-CAT)	X	X			X	X	X	X	X
Physician Global Assessment Improvement Scale (GAIS) and physician global assessment	X				X	X	X		
Subject's Satisfaction questionnaire for SMF appearance	X g				X	X	X		
Subject's impact questionnaire	X				X	X	X		
Subject Global Assessment of Change and subject self assessment	X				X	X	X		
2D Standardized photography	X		X	X	X	X	X	X	X
MRI	X f						X		
AEs		X	X	X	X	X	X	X	X

- a. Study day is based on Day 0 defined as the day of RZL-012 injection.
- b. Including Fitzpatrick skin type, height, BMI
- c. A serum ( $\beta$ -hCG) pregnancy test will be administered to females of childbearing potential at screening and a urine pregnancy test will be administered at baseline prior to dosing
- d. In case of clinically significant values at any visit, an unscheduled visit will be added
- e. Pre/post – refers to before/after injection, respectively
- f. MRI (performed during screening period) will be conducted after subject qualifies on all screening criteria within a window of 10 days from the visit in the clinic. Post-treatment period MRI will be completed 84 days ( $\pm$  7 days) after the subject's last treatment session.
- g. Subjects will be asked on their neck appearance satisfaction at screening visit
- h. Physical exam will be done only to the treated area

 Statistics in Medicine	DOCUMENT NUMBER: 140-BST-PLN-001	PAGE: 12 of 16
TITLE: Statistical Analysis Plan of Protocol Number RZL-012-SMF-P2bUS-001	EFFECTIVE DATE : 08/03/2022 REVISION NUMBER : 1.0	

- **Rationale Sample Size Calculation**

For the primary endpoint (proportion of high dose group subjects who have at least a 1-grade improvement from baseline to Day 84 on the C-CAT scale), the assumed true rates are 70% in the RZL-012 high dose group and 35% in the placebo group (a difference of 35 percentage points). Based on the use of a two-sided test of equality of binomial proportions at the alpha=0.05 level of significance, 41 subjects per group are required at 90% power. In order to account for a dropout rate of up to ~9%, the planned sample size is 45 subjects per group, for a total sample size of 135 subjects.

- **Statistical Analysis Software and Data Management**

Data manipulation, tabulation of descriptive statistics, calculation of inferential statistics, and graphical representations will be performed using SAS® version 9.4 or higher for Windows. If the use of other software is warranted, the final statistical methodology report will detail what software was used for what purposes.

- **Data Management**

Data management for the study is performed by Medistat.

- **Medical Coding**

Concomitant medications entered into the database are coded using the WHO (World Health Organization) Drug Public Website Dictionary named WHOCC-ATC/DDD index, which employs the Anatomical Therapeutic Chemical classification system.

Adverse events are coded using the most updated version of Medical Dictionary for Regulatory Activities (MedDRA) terminology.

Medical history events are coded using the most updated version of Medical Dictionary for Regulatory Activities (MedDRA) terminology.

- **Handling of Missing data**

Every effort will be made to obtain all data from all subjects who have been enrolled, to minimize missing data.

A subject with missing primary endpoint data will be imputed as treatment failure.

- **Subject Population for analyses**

MediStat Statistics in Medicine	DOCUMENT NUMBER: 140-BST-PLN-001	PAGE: 13 of 16
TITLE: Statistical Analysis Plan of Protocol Number RZL-012-SMF-P2bUS-001	EFFECTIVE DATE : 08/03/2022 REVISION NUMBER : 1.0	

The Intent-to-treat population (ITT) will consist of all enrolled subjects who received the study treatment, (exposed population), including subjects prematurely withdrawn. The ITT population will serve as the principal data analysis set for analyses of efficacy and safety endpoints. Subjects will be analyzed according to the treatment received

The Per-Protocol population (PP) will consist of all subject included in the ITT population who were rated for both S-CAT and C-CAT on both baseline and day 84 visits. The PP population will serve as a sensitivity analysis of the efficacy endpoints.

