Statistical Analysis	
A sample size of 135 subjects will be included in the study, divided into three (3) groups: RZL-012 low dose (up to 183.6 mg/5.4 mL), RZL-012 high dose (up to 270 mg/5.4 mL) and placebo (up to 5.4 mL), with 45 subjects in each group.
 
For the primary endpoint (proportion of high-dose group subjects who have at least a 1-grade improvement from baseline to day 84 on the C-CAT scale), the assumed true rates are 70% in the RZL-012 high dose group and 35% in the placebo group (a difference of 35 percentage points). Based on the use of a two-sided test of equality of binomial proportions at the alpha=0.05 level of significance, 41 subjects per group are required at 90% power. In order to account for a dropout rate of up to ~9%, the planned sample size is 45 subjects per group, for a total sample size of 135 subjects.
 
Secondary endpoints (improvement in 1 point in S-CAT and C-CAT, improvement in 2 points in both S-CAT and C-CAT) will be tested using a two-sided test of equality of binomial proportions at the alpha=0.05 level of significance. If the primary analysis is not statistically significant, then the results of the secondary analysis will be exploratory rather than confirmatory. All secondary endpoints will be tested using a two-sided test at the alpha=0.05 level of significance.
 
All other secondary endpoints will be tested using a two-sided test at the alpha=0.05 level of significance.
 
All measured variables and derived parameters will be listed individually and, if appropriate, tabulated by descriptive statistics.
 
For categorical variables, summary tables will be provided giving sample size, absolute and relative frequency, and 95% confidence interval (CI) for proportions by study arm.
 
For continuous variables, summary tables will be provided giving sample size, arithmetic mean, standard deviation, coefficient of variations (CV%), median, minimum and maximum, and 95% CI for means of variables by study arm.
 
The data will be analyzed using the SAS version 9.4 (SAS Institute, Cary North Carolina).
 
For the primary endpoint analysis, Pearson's chi-square test will test the statistical significance of the difference in the proportion of responding subjects between the high dose RZL-012 group and the placebo group. A responder is defined as a subject who has at least a 1-grade improvement between Day 84 and baseline on the C-CAT.

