## **12.0 STATISTICAL CONSIDERATIONS**

### **12.1 Sample Size Determination**

A total of 135 subjects will be included in the study, divided into three (3) groups: RZL-012 low dose (up to 183.6 mg/5.4 mL), RZL-012 high dose (up to 270 mg/5.4 mL) and placebo (up to 5.4 mL) with 45 subjects in each group.

For the primary endpoint (proportion of high dose group subjects who have at least a 1-grade improvement from baseline to Day 84 on the C-CAT scale), the assumed true rates are 70% in the RZL-012 high dose group and 35% in the placebo group (a difference of 35 percentage points). Based on the use of a two-sided test of equality of binomial proportions at the alpha=0.05 level of significance, 41 subjects per group are required at 90% power. In order to account for a dropout rate of up to ~9%, the planned sample size is 45 subjects per group, for a total sample size of 135 subjects.

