The Chi-Square test will be applied to test the statistical difference between the placebo group and the RZL-012 high-dose group in responder rate at Day 84. Responder rate is defined as the percentage of subject achieving at least a 1-grade improvement from baseline in C-CAT.

- **Analysis of secondary Endpoints**

Secondary endpoints (improvement in 1 point in S-CAT and C-CAT, improvement in 2 points in both S-CAT and C-CAT) will be tested using a two-sided test of equality of binomial proportions at the alpha=0.05 level of significance.

All other secondary endpoints will be tested using a two-sided test at the alpha=0.05 level of significance.

- The Chi-Square test will be applied to test the statistical difference between the placebo group and each of the RZL-012 dose groups in the responder rate at Day 84 where responder rate is defined as the percentage of subject achieving at least a 1-grade improvement from baseline in both S-CAT and C-CAT.
- The change and percentage of change from baseline at Day 84 in SMF thickness measured with caliper and in SMF volume by MRI will be calculated along with 95% Confidence intervals.

The Paired T-test for two means (paired observations) will be applied for testing the statistical significance of the change and percentage of change from baseline at Day 84 in SMF thickness measured with caliper and in SMF volume by MRI within each study group.

MediStat Statistics in Medicine	DOCUMENT NUMBER: 140-BST-PLN-001	PAGE: 15 of 16
TITLE: Statistical Analysis Plan of Protocol Number RZL-012-SMF-P2bUS-001	EFFECTIVE DATE : 08/03/2022 REVISION NUMBER : 1.0	

The two-sample T-test for independent samples will be applied for testing the statistical significance of the change and percentage of change from baseline at Day 84 in SMF thickness measured with caliper and in SMF volume by MRI between each of the RZL-012 dose groups and the placebo group.

- Analysis of Exploratory endpoint
  - SMF improvement

The SMF improvement using the Global Aesthetic Improvement Scale (GAIS) , the physician Global Assessment of Change Scale, Subjects Global Self-Assessment of Change Scale, Subject Global Assessment of Change Scale, the subject's satisfaction questionnaires, and the subjects's impact questionnaire will be summarized at each timepoint and by treatment group.

- Analysis of Safety

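### The 90% power assumes that dropouts leave the analysis; the SAP scores them as failures among 45 per arm, which gives about 87% at the planned dropout rate

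*SAP*

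**What the plan says.** The sample-size paragraph is essentially the same in the Protocol Synopsis (Statistical Analysis), Protocol 12.1 and SAP section 5 (Rationale Sample Size Calculation). It takes these planning values: "the assumed true rates are 70% in the RZL-012 high dose group and 35% in the placebo group". With a two-sided test at 0.05 it concludes that "41 subjects per group are required at 90% power". It then adds: "In order to account for a dropout rate of up to ~9%, the planned sample size is 45 subjects per group".

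SAP section 5 (Handling of Missing data) sets the rule for the primary endpoint: "A subject with missing primary endpoint data will be imputed as treatment failure". Under Subject Population for analyses, the ITT set is every enrolled subject who received study treatment, including those who withdraw early, and it is the principal set for efficacy. The per-protocol set, which requires C-CAT and S-CAT ratings at both baseline and Day 84, is a sensitivity analysis only.

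The protocol has no missing-data rule for the primary endpoint. SAP section 6 (General) says that the SAP prevails on how data are handled and analysed. Treatment is a single session on Day 0.

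**The concern.** Going from 41 to 45 is the usual inflation for subjects who will be lost from the analysis: enrol 45, lose 4, analyse 41. The planned primary analysis does not lose them. Anyone dosed on Day 0 who has no Day 84 C-CAT stays in the denominator as a non-responder, so dropout pulls both responder rates towards zero and shrinks the difference between them. Dividing n by (1 − d) does not make up for a difference multiplied by (1 − d).

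The power quoted for the primary comparison is therefore not the power of the primary analysis at the dropout rate the plan says it covers. Under Protocol 12.3 the secondary results become exploratory if the primary test fails, so this probability of success should be stated for the analysis that will be run. Failure imputation also makes power sensitive to unequal dropout, and the sample-size paragraph gives no sign of that.

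**Working it through.** **Inputs.** Responder rates 0.70 and 0.35, two-sided alpha 0.05, power 90%, 41 then 45 per arm, dropout up to about 9% (Protocol 12.1; SAP section 5). Equal allocation (SAP section 5, Study Design). Chi-square test of high dose against placebo (SAP section 6). Missing counted as failure, all treated subjects analysed (SAP section 5). I take d = 4/45 = 8.9% for the dropout rate, because it turns 45 into exactly 41.

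**Step 1: reproduce the plan's figures.** The pooled-variance formula without continuity correction is

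n = [1.960·√(2·p̄·(1−p̄)) + 1.282·√(p1(1−p1) + p2(1−p2))]² / (p1−p2)²

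With p̄ = 0.525:

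n = [1.960·√0.49875 + 1.282·√0.4375]² / 0.35² = (1.384 + 0.848)² / 0.1225 = 40.66, so 41.

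Power is 89.5% at n = 40 and 90.2% at n = 41. For dropout, 41/(1 − 4/45) = 45 and 41/0.91 = 45.05. Both stated figures reproduce.

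**Step 2: apply the SAP's missing-data rule.** With 4 of 45 per arm scored as failures:

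- high dose: 0.70 × 41/45 = 0.638
- placebo: 0.35 × 41/45 = 0.319
- difference: 0.35 × 41/45 = 0.319

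**Step 3: power at 45 per arm, same formula.** With p̄ = 0.4783:

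z = [0.3189·√45 − 1.960·√0.4991] / √0.4482 = (2.139 − 1.385) / 0.669 = 1.127, so power = 87.0%.

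The variance terms hardly move. What falls is the difference times √n: from 0.35·√41 = 2.241 to 0.3189·√45 = 2.139, a factor of √(41/45) = 0.955.

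**Step 4: check without the normal approximation.** I enumerated all outcomes of the Pearson test.

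| Analysis | Formula | Exact |
|---|---|---|
| 41 per arm, dropouts removed | 90.2% | 91.5% |
| 45 per arm, no dropout | 92.7% | 92.0% |
| 45 per arm, 4/45 dropout risk, counted as failures | 87.0% | 86.1% |
| 45 per arm, exactly 4 dropouts in each arm, counted as failures | – | 87.4% |

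**Step 5: vary the dropout rate** (45 per arm, equal dropout, counted as failures).

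| Dropout | Formula | Exact |
|---|---|---|
| 3% | 91.0% | 90.2% |
| 4.5% | 90.1% | 89.2% |
| 5% | 89.7% | 88.9% |
| 9% | 86.9% | 86.0% |
| 10% | 86.2% | 85.2% |

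**Step 6: size needed for 90% at d = 4/45.** The formula gives 49.5, so 50 per arm (49 gives 89.7%, 50 gives 90.3%). Exact enumeration reaches 90.3% at 49.

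**Step 7: unequal dropout.** The documents give no split by arm, so these are illustrations with the same total of 8 dropouts, using the formula. With 6/45 (13.3%) in high dose and 2/45 (4.4%) in placebo, power is 74.3%. With the split reversed, it is 94.8%.

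**The case against.** The strongest objection is that the documents call 70% and 35% the assumed true rates and never say that they refer to completers. If they already count dropouts as failures, 45 per arm gives 92.7% and there is no shortfall. This matters, because the 87% depends on the completer reading. But on the other reading no dropout allowance would be needed: 41 would suffice, and the step to 45 would have no purpose. The inflation makes sense only if the rates are among subjects with Day 84 data. On either reading the sample-size paragraph and the missing-data rule do not fit together as written.

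Second, 9% is a ceiling, and the loss is small below it: at 5% dropout the formula still gives 89.7%. That is so, but the plan presents 45 as sufficient up to about 9%, and under its own analysis it is sufficient to about half that or less.

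Third, the threshold depends on the method. It is about 4.5% by the formula and about 3% by enumeration, so any restated figure should name its method. Unequal dropout can also raise power as well as lower it, and neither document supports a direction. Both points stand.

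Fourth, three points is modest, the stated arithmetic is correct, and failure imputation is a legitimate conservative rule. All true. They bear on how much to change, not on whether the stated power is right.

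**Conclusion.** The concern holds. The plan's 41 and 45 are computed correctly, but they describe an analysis from which dropouts are removed. For the primary analysis the SAP specifies, power at the full dropout allowance is about 87% (87.0% by the plan's formula, 86.1% exact, 87.4% with exactly 4 dropouts per arm), not 90%.

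This rests on three assumptions: that 70% and 35% are rates among subjects with Day 84 data, that dropout reaches about 9%, and that it is equal in the two arms and occurs after dosing. The shortfall is about 3 points under these conditions and shrinks with lower dropout. Unequal dropout could move power well away from 87% in either direction. The type I error, the test and the analysis set are unaffected.

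**What to change.** Keep the missing-data rule, the analysis set and the enrolment. In the Protocol Synopsis, Protocol 12.1 and SAP section 5:

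- State that 70% and 35% are the assumed rates among subjects with a Day 84 C-CAT. If they are meant as all-treated rates, say so and drop the dropout allowance as the reason for 45.
- Replace the power sentence with wording such as: *With 45 subjects per group, 9% dropout in each group and missing Day 84 C-CAT counted as failure (analysed rates about 63.8% and 31.9%), power is about 87% by the pooled-variance formula; 90% is retained for dropout up to about 4.5% by that formula, or about 3% by exact calculation.*
- Preferably add one sentence saying that unequal dropout between arms moves power in either direction, with both illustrations from step 7.

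The cost is wording in three places and a slightly less favourable stated power. If the sponsor prefers to keep 90% at 9% dropout, the alternative is about 50 per arm (150 in total), but this point does not ask for that.
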